## Protocol

Preterm infants will be recruited at gestational age 240/7-286/7 weeks GA. Each infant will be randomized to receive either the PULSED NTrainer or SHAM intervention using a software random integer function in Minitab v.17 (www.minitab.com). As shown in Figure 1, infants assigned to the PULSED NTrainer group will receive a progressive dose of the pulsatile orocutaneous stimulation. Beginning at 30 weeks' PCA, these infants will receive 2 weeks of low-dose PULSED NTrainer stimulation (2 x 3-minute blocks) with a 1-minute stimulus 'off-period' between the stimulation blocks. This form of stimulation will be given simultaneous with tube feedings 3 times/day. The stimulus dose will then be increased over the next 2 weeks (3 x 3-minute blocks of PULSED NTrainer stimulation) with a 1-minute stimulus 'off-period' between the stimulation blocks, also given simultaneously with tube feedings 3 times/day. Preterm infants randomized to the SHAM condition will be given a regular silicone pacifier during tube feedings over the same time period.

## Intervention and Outcome Variables

[figure not shown]

Figure 1. Somatosensory intervention plan for preterm infants along with the salivary sampling protocol and digitized measurements of non-nutritive suck progression is shown above. Primary (salivary gene expression), and secondary (transition to full oral feed, oromotor NNS pattern formation, NICHD Neonatal Research Network feeding-growth questionnaire, and Bayley III screener at NICU follow-up) outcome variables are given.

## Orocutaneous Stimulation Regimen

The NTrainer PULSED orocutaneous stimulus consists of a series of 6-cycle bursts which are delivered by a servo-controlled pneumatic amplifier (NTrainer System®) to the lumen of a standard silicone pacifier (e.g., WeeSoothe, or Soothe). These pneumatic bursts are frequency modulated (FM) from 2.8 to 1.6 Hz across the 6-cycle structure with a 2-second

pause period between bursts (Figure 2). Individual pressure cycles have a 31 millisecond (ms) rise/fall time to ensure a salient stimulus spectra with significant energy from DC-16 Hz. Frequency modulation is a physiologic feature of the non-nutritive suck (NNS) in preterm infants. A total of 34 bursts are presented in a 3-min block. A 1-minute rest period (no stimulation) occurs between stimulation blocks. Criteria for initiation of orocutaneous therapy include the following: 1) stable vital signs and not on continuous vasopressor medications; 2) tolerating enteral feeds in previous 48 hours; and 3) not intubated and mechanically ventilated. If the infant is on nasal intermittent positive pressure ventilation, continuous positive airway pressure or nasal cannula >2 liters per minute, then the FiO2 must be <40%.

[figure not shown]

Figure 2. Preterm infant receiving PULSED NTrainer stimulation during gavage feeding in the NICU. NG tube is placed through the left nares (not visible). Pneumatic stimulus control signals and output through the pacifier nipple are shown in the left panel. a) voltage-controller gate signal, b) intraluminal pressure (inside) the nipple, and c) mechanical displacement at the nipple cylinder wall.

### **NNS Assessment and Automated NNS Digital Signal Processing and Feature Extraction**

In addition to the oral stimulation interventions (PULSED NTrainer vs. SHAM pacifier), all study infants will be assessed 3 times/week (e.g., Mon/Wed/Fri) for NNS performance. The NTrainer System® will be used in 'assessment mode' to record the compression dynamics of NNS during a 3-minute session to immediately precede a tube feeding that is not associated with an intervention condition.

The most active 2-minute period of NNS behavior based on suck cycle count is automatically extracted from each suck assessment data file using an automated waveform feature extraction algorithm on the NTrainer System®. The NNS pressure waveform is band-pass filtered (0.5-20 Hz) to remove low frequency offsets due to tongue/jaw posturing and thermal drift associated with oral contact on the pacifier bulb, and to remove high-frequency jitter. Pressure peaks > 1.6 cm H2O are subjected to feature extraction criteria, including suck cycle symmetry, cycle duration, and burst identification defined as two or more NNS events occurring within 1200 ms.

This algorithm permits objective identification of NNS burst activity distinct from non-NNS mouthing compressions or tongue thrusts against the pacifier. Four measures will be objectively extracted from the indexed records of suck compression, including (1) NNS Bursts/min where an individual burst includes 2 or more suck cycles, (2) NNS Cycles/min, (3) NNS Spatiotemporal Index, and (4) NNS compression pressure (cm H2O).

### **PO Feeding Advancement**

Preterm infants will advance on a standardized cue-based feeding schedule utilized by each site NICU, known as Infant Driven Feeding® that will lead to full nipple feeds. This standardization of oral feeding advancements across sites will limit confounders that may ultimately skew the data.

Preterm infant participant data will be managed with our Neonatal Oromotor Database, a custom software developed in the [name] laboratory specifically for NTrainer studies in the NICU. This database software is compatible with MS WIN operating systems, and is password-protected and coded as an executable for MS ACCESS 2013. This software provides a paperless, efficient system for NICU study personnel to log daily information including GA, growth parameters, medications, oxygen requirement, feeding history, medical procedure log, comments, as well as NTrainer/SHAM and salivary sampling dates on enrolled infants.

### **Saliva Collection, Processing, and Gene Expression Analysis**

*Saliva Collection:* Saliva samples will be collected from all enrolled infants on the first day prior to receiving either the SHAM or PULSED NTrainer intervention. This sample will serve as our baseline gene expression profile. Samples will then be obtained twice per week (~3 day intervals) up to the time of achievement of full oral feeds or discharge home from the hospital with either a nasogastric tube (NG) or gastrostomy tube.

Saliva samples at each site will be collected with techniques that have been optimized and validated through the [name] laboratory. Briefly, saliva samples will be collected with a 1 mL syringe, end caps removed and attached to low wall suction. Saliva will be collected for approximately 20 seconds and immediately stabilized in 500 µL of Qiagen's RNA Protect Saliva to halt gene expression changes, inhibit destructive RNases, and limit microbial overgrowth. Samples will be vortexed briefly and frozen at -20°C. Once frozen, samples are stable for up to 18 months prior to the need for total RNA extraction. Thus, samples from Nebraska and Santa Clara will be shipped once a month on ice overnight to the [name] laboratory at the Mother Infant Research Institute at Tufts Medical Center in Boston, MA for processing.

*Generation of a Saliva Biobank:* One additional saliva sample will be obtained each week from all enrolled subjects to generate a biobank repository. The rationale for this approach is twofold. First, it is possible that during shipment or processing, salivary RNA may be destroyed and not be of sufficient quality to incorporate into the study. Prior studies from this lab have demonstrated a 10% failure rate of gene amplification in saliva samples. Banking an additional sample each week from study subjects will ensure that we will limit loss of data points. Second, we anticipate that there are informative salivary biomarkers of oral feeding maturation that have yet to be identified. By generating a biobank of additional saliva samples that may be retrospectively interrogated on either a microarray gene expression platform or with RNASeq, we will have the potential to discover novel hypotheses about gene-gene interactions and/or transcriptional regulatory processes related to oral feeding in the preterm population.

**Total RNA Extraction:** Salivary samples will be extracted for total RNA using established protocols optimized in the [name] laboratory. RNA extraction will occur with the QIAGEN RNeasy Protect Saliva Mini kit per manufacturer's instructions. On-column DNase treatment will be performed for each sample to eliminate genomic DNA contamination. Samples that are part of the biobank will be frozen at -80°C pending need for future analysis. Samples that will be used for RT-qPCR experiments will first undergo cDNA conversion with the Life Technologies SuperScript® Vilo™ kit per manufacturer's instructions. cDNA will be stored at -80°C in the Mother Infant Research Institute at Tufts Medical Center pending gene expression analysis.

**Gene Expression Analysis:** For the purpose of this study, we will interrogate each sample for nine genes, six target genes of interest and three reference genes for quality control and potential normalization of gene expression data. Genes to be analyzed in this study have been previously shown to be directly linked to oral feeding in the newborn and include *CDH13*, *FOXP2*, *NPHP4*, *NPY2R*, *PLXNA1*, and *WNT3*. The three reference genes include *GAPDH*, *HPRT1*, and *YWHAZ*, all of which have been shown to maintain stable gene expression across advancing PCA. All cDNA samples will undergo a targeted pre-amplification with a custom TaqMan® PreAmp Master Mix for all nine genes. This targeted approach to amplification will ensure that only those genes of interest will be amplified and not all genes across the transcriptome which may introduce bias. Pre-amplified cDNA will then undergo PCR with TaqMan® Fast Advance Master Mix on the Life Technologies Quant Studio™ 7 Flex Real-Time PCR System. This instrument is housed with the Mother Infant Research Institute at Tufts Medical Center and is an advanced state-of-the-art PCR machine and software system. All efforts will be made to adhere to the Minimum Information for Publication of Quantitative Real-Time PCR Experiments (MIQE) guidelines for this study. All samples will be run in duplicate with appropriate positive and negative controls.

**Initial Gene Expression Analyses:** All gene expression data will be normalized on the Quant Studio™ 7 Flex Real-Time PCR System. Only samples that have successful amplification of all three reference genes will be considered in the analysis. Previously, genes have been informative in a binary fashion (+/- expression). However, for the purpose of this study, we will be prepared to calculate relative gene expression of each target gene with the delta delta cycle threshold ( $\Delta\Delta Ct$ ) method. In accordance to the MIQE guidelines, we will use the three reference genes for normalization and determine a geometric mean of their Ct in each sample to calculate relative gene expression. Normalized data will then be given to our statistician and bioinformatic collaborator for analysis.

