Official Title: Somatosensory Modulation of Salivary Gene Expression and Oral Feeding in Preterm Infants

NCT number: NCT02696343

Document Date: 3-31-24

Statistical Analysis Plan.

Primary Outcome: Gene Expression

In this randomized controlled clinical trial, we analyzed salivary developmental gene expression changes in extreme and very preterm infants randomized to receive either therapy with the NTrainer feeding system or a 'Sham' mode (blind pacifier) to assess the effect of therapy on the developing infant. Salivary samples were collected at a series of timepoints, beginning with the initiation of therapy through the learning process of oral feeding or to transfer to an outlying hospital. The primary goal of this study was to assess and compare differences in gene expression patterns over time between groups. The expression of six genes involved in 1.) memory: *CDH13*; oral development: *FOXP2* and *WNT3*; 3.) sensory integration: *NPHP4*, and *PLXAN1*; and hunger signaling: *NPY2R*, along with two reference genes for proper normalization were measured via RT-qPCR for each subject at 6 timepoints. The raw CT values were normalized for each subject and timepoint by subtracting the geometric mean of the reference genes from the mean expression of each gene (deltaCT). These deltaCT values were used for the remainder of the analysis. A positive deltaCT value indicates that the target gene had lower expression than the reference gene; conversely increasing deltaCTs are indicative of decreasing expression. In order to determine changes in gene expression, one way and two-way ANOVA analysis in R [1] was used. Initially, the analysis was done to assess expression pattern changes over time for 1.) the cohort as a whole, 2.) based on treatment status, and 3.) by sex. Given that the timepoint measurements are done on the same subject, repeated measure ANOVA and subject for which all time points were not measured were excluded from the analysis. Subsequently, the analysis was extended by grouping subjects by bronchopulmonary dysplasia (BPD) status, looking at the effect over time, the effect of treatment status and the interaction of the two. BPD was defined based on NIH criteria.

Secondary Outcomes: Non-nutritive Suck Dynamics and Growth in Daily Oral Feeds

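### The SAP gives no rule for a target gene with no Ct; if that counts as missing, the complete-case primary analysis selects infants on the outcome

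*Protocol*

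**What the plan says.** Three statements bear on this point.

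- **Sample gate.** Under Initial Gene Expression Analyses, the protocol sets one condition for a usable sample: "Only samples that have successful amplification of all three reference genes will be considered in the analysis". Nothing comparable is set for the six target genes, so a sample whose references amplify and whose target does not passes the gate.
- **Form of the outcome.** The same paragraph says "Previously, genes have been informative in a binary fashion (+/- expression". It then moves towards a quantitative measure, worded as readiness: "we will be prepared to calculate relative gene expression of each target gene with the delta delta cycle threshold". The SAP (Primary Outcome) settles on deltaCT, obtained by "subtracting the geometric mean of the reference genes from the mean expression of each gene (deltaCT", and continues: "These deltaCT values were used for the remainder of the analysis". A higher deltaCT means lower expression. The SAP contains no detected/undetected analysis.
- **Incomplete series.** Each gene is measured at six time points and analysed by one-way, two-way and repeated-measures ANOVA. For the repeated measures the SAP states: "subject for which all time points were not measured were excluded from the analysis".

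Neither document says whether a target with no Ct is missing, set to a limit, or censored.

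**The concern.** DeltaCT is a difference between a target Ct and a reference value. With no target Ct there is no deltaCT unless one is assigned. The protocol's account of earlier work means that non-expression of these genes is a foreseeable result and not just a laboratory mishap, so the plan needs a rule for it.

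If the rule was to leave the value blank, one non-detect in six visits removes the infant from that gene's analysis. The cause of removal is then low expression, which is the outcome itself. When treatment changes expression, the arms lose different numbers of infants, and those who remain are the higher expressers of each arm. The estimated difference shrinks and power falls. Information on whether a gene was on or off is also not analysed.

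**Working it through.** **The plan's own figure.** The SAP gives 110 infants for 80% power, under Secondary Outcomes. With λ = N·m·f²/(1−ρ), N = 110, f = 0.10, ρ = 0.60 and m = 4 measures, λ = 110 × 4 × 0.01 / 0.40 = 11.0. On 3 and 324 degrees of freedom, with alpha 0.05, power is 0.799, and 80% needs N = 111. Alpha and m are my assumptions. The figure reproduces, and this point does not depend on it.

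**Inputs.**
- Six time points: SAP, Primary Outcome.
- Correlation 0.60 and 114 infants: SAP, Secondary Outcomes, borrowed here for the gene data. I assume an even split, 57 per arm.
- Assumed, because the documents are silent: non-detect rates of 1% to 30% per sham sample, a 0.5 SD shift toward higher expression at time points 2 to 6, and non-detects treated as missing.

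**Loss without correlation.** The share of infants complete for one gene is (1−p)⁶: 94% at p = 1%, 74% at 5%, 53% at 10% and 26% at 20%. Positive within-infant correlation softens this.

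**Power with no loss.** Take the two-arm contrast of change, defined as the mean of the five later values minus baseline. Its SD is √[(1−0.6)(1+1/5)] = 0.693, so the standardised effect is 0.5/0.693 = 0.722. The noncentrality is 0.722 × √(57/2) = 3.85, and power is about 97%.

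**Loss through non-detects.** In simulation, each infant has six deltaCT values with SD 1 and correlation 0.6. A value above a fixed cut-off is a non-detect, and only infants with six detected values are kept.

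| Assumed sham non-detect rate | Kept, sham v NTrainer | Shrinkage of change effect | Power |
|---|---|---|---|
| 1% | 96% v 98% | about 1% | 96% |
| 5% | 83% v 91% | about 5% | 93% |
| 10% | 71% v 83% | about 9% | 90% |
| 20% | 52% v 68% | about 13% | 78% |
| 30% | 38% v 54% | about 17% | 63% |

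At 10% this is about 40 sham infants (57 × 0.71) against 47 NTrainer infants (57 × 0.83).

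**Sensitivity.**
- The post-baseline difference in level suffers more than the change contrast. It shrinks by about 30%, 40% and 46% at 10%, 20% and 30%.
- If treatment lowers expression by 0.5 SD, the imbalance reverses. At 10%, 71% of sham and 52% of treated infants are kept, and the change effect falls from 0.50 to 0.45 SD.
- With no treatment effect, both arms lose the same share and the arm difference is unbiased.
- Removing the same number of infants at random gives power of about 92%, 84% and 70% at 10%, 20% and 30%, against 91%, 79% and 64% in the same run with outcome-dependent removal. Selection itself therefore costs roughly 1 to 6 points; the rest is ordinary complete-case loss.

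**The case against.** The strongest reply is that the SAP never says a non-detect is missing. A sample that was collected, passed the reference-gene gate and was run in duplicate can fairly be called measured even if one target gave no Ct. The exclusion may have been meant for missed samples, spoiled RNA or infants transferred elsewhere. Had non-detects been set to the cycle limit, no infant would be dropped on this ground, and in the simulation power for the change contrast stays near 97%. This stands, and it is why the point is conditional. A reader might infer that the SAP does drop the lowest expressers; the text does not support that.

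Two other inferences also go too far.
- A reader might say that the SAP abandons a promised on/off analysis. The protocol's remark concerns earlier work, the next sentence prepares for a quantitative measure, and no binary analysis is promised.
- A reader might take the protocol's 10% amplification failure figure as the non-detect rate. It is given as a reason for banking spare saliva, in a passage about RNA quality, and says nothing about non-expression. The 10% row above is an assumption.

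It is also fair to say that targeted pre-amplification of all nine genes may keep non-detects rare, that harm at 1% is negligible, and that the simulated contrast is not the SAP's ANOVA.

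The objection does not remove the silence. Missing, limit and censored handling give different primary results from the same data, and a reader cannot tell which was used.

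**Conclusion.** The point holds in conditional form. The primary analysis has no stated way to handle a target gene with no Ct, and its complete-case rule would turn such results into outcome-dependent exclusions if they were left blank. The consequence is attenuation and lost power when treatment has an effect; the calculations show no bias in the arm contrast when it has none.

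The size cannot be fixed from the documents. Over assumed sham non-detect rates of 1% to 30%, the change effect shrinks by about 1% to 17% and power falls from about 97% to between 96% and 63%. These figures rest on 57 per arm, a 0.5 SD shift, a correlation borrowed from the secondary outcomes, a fixed detection cut-off and the missing-value reading. The change is advisable, not essential, because the true non-detect rate may be small.

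**What to change.** 1. State how a target with no Ct was handled in samples whose reference genes amplified, and report detection rates by gene, arm and time point. If non-detects prove very rare, little more is at stake on this ground.
2. For each gene, replace the complete-case repeated-measures ANOVA with a mixed model for deltaCT that keeps every infant with any valid sample. Treat a non-detect as right-censored at the deltaCT implied by the maximum cycle, not as missing.
3. As a supporting analysis, fit a mixed-effects logistic model for detected/undetected by arm, time and arm-by-time.
4. Reconcile the number of reference genes, three in the protocol and two in the SAP, since that gate separates poor RNA from true non-expression.

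The cost is SAP wording and one extra model per gene on existing data, with no new assays. The censored model relies on a distributional assumption, which is a small price. The SAP is written in the past tense, so if results have been seen, the revised models should be labelled as added afterwards.

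### Reference-gene Cts are to be averaged geometrically although Ct is already a log scale, so deltaCT does not cancel sample input exactly; the leak is small

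*Protocol*

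**What the plan says.** The Protocol, under Initial Gene Expression Analyses, plans relative quantification: "we will be prepared to calculate relative gene expression of each target gene with the delta delta cycle threshold" method. The reference genes are combined sample by sample, and the text names the scale, since the analyst is to "determine a geometric mean of their Ct in each sample to calculate relative gene expression".

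The SAP, under Primary Outcome: Gene Expression, reports the step as done. It starts from the unprocessed CTs of every sample and forms the analysis variable by "subtracting the geometric mean of the reference genes from the mean expression of each gene (deltaCT"). On the use of the result it adds: "These deltaCT values were used for the remainder of the analysis". The normaliser therefore enters every ANOVA of the primary outcome.

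Neither text says that Ct is converted to a linear quantity before the geometric mean is taken. Neither gives reference-gene Ct values, RNA yields, a fixed cDNA input or amplification efficiencies.

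**The concern.** Normalising is meant to remove differences in the amount of RNA that entered the assay. Lower input delays every gene by about the same number of cycles, so a sound deltaCT should not change. This holds exactly when the reference Cts are averaged arithmetically. It fails, if only slightly, when they are averaged geometrically, because that takes a log-type mean of values that are already logs.

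Input can plausibly vary here. The Protocol says: "Saliva will be collected for approximately 20 seconds and immediately stabilized in 500 µL" of stabiliser, which fixes the time and the stabiliser but not the volume of saliva. If yield changed as infants matured, the residue would have the same sign in all six target genes and could look like a shared time trend. If yield also differed by arm, it would enter the comparison of patterns between groups.

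**Working it through.** The documents state no figure for the normaliser, so there is none to reproduce. The check is algebra, then numbers under assumed reference Cts.

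**Which mean belongs on which scale.** Taking two-fold amplification per cycle, quantity is proportional to 2^-Ct. For k reference genes the geometric mean of the quantities is (∏ 2^-Ct_i)^(1/k) = 2^-(ΣCt_i / k). Its value on the Ct scale is the arithmetic mean (AM) of the Cts.

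**Response to input.** Let lower input add c cycles to every gene.
- AM(Ct + c) = AM(Ct) + c, so deltaCT is unchanged.
- For the geometric mean (GM), the derivative with respect to Ct_i is GM / (k × Ct_i). Summed over genes this is GM/HM, where HM is the harmonic mean. GM/HM exceeds 1 unless all reference Cts are equal.
- The drift in deltaCT is therefore about -c × (GM/HM - 1). Low-input samples get a deltaCT that is slightly too low, which reads as higher expression.

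**Worked case, assumed Cts 15/22/29.** AM = 22.00, GM = 21.231, HM = 20.463.
- Leak per cycle: 21.231/20.463 - 1 = 0.0375.
- Gene weights GM/(3 × Ct): 0.472, 0.322 and 0.244. They sum to about 1.038, not 1, and the lowest-Ct gene has nearly twice the weight of the highest.
- For c = +3 (an 8-fold fall in input): GM(18, 25, 32) = 24.329. Drift = -(24.329 - 21.231 - 3) = -0.098 cycles, and 2^0.098 = 1.07, or 7% in fold terms.

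**Range of assumed reference Cts.**

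| Reference Cts (assumed) | AM - GM | Leak per cycle | deltaCT drift at c = +3 |
|---|---|---|---|
| 20/22/24 | 0.061 | 0.3% | -0.007 |
| 18/22/26 | 0.245 | 1.1% | -0.030 |
| 18/25/28 | 0.397 | 1.8% | -0.048 |
| 15/22/29 | 0.769 | 3.7% | -0.098 |
| 12/22/32 (extreme) | 1.633 | 8.7% | -0.222 |
| 8/14/20 (very low Cts) | 0.916 | 7.5% | -0.178 |
| 20/24 (two genes) | 0.091 | 0.4% | -0.011 |
| 18/26 (two genes) | 0.367 | 1.7% | -0.045 |
| 15/30 (two genes, wide) | 1.287 | 6.1% | -0.159 |

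Two-gene sets are included because the SAP describes six targets "along with two reference genes for proper normalization were measured via RT-qPCR", whereas the Protocol lists three. That mismatch is a separate point. The very-low-Ct set is included because the Protocol pre-amplifies all cDNA. The leak per cycle is the local slope. Drift is somewhat larger when input rises: for 15/22/29, c = -3 gives +0.133.

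The AM - GM offset is close to constant across samples and cancels in comparisons between times or arms. Only the input-dependent part can matter.

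**Practical effect.** A simulation used reference sets 20/22/24, 18/22/26 and 15/22/29, reference error SD 0.5, target SD 1.5 and input SD 1 to 3 cycles (all assumed). The two versions of deltaCT correlated at 0.995 to 0.9999. The geometric version had 0.04% to 1.4% more variance. Its correlation with input was -0.004 to -0.08, against about 0 for the arithmetic version.

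**The case against.** The strongest reply is that the wording is shorthand. The SAP speaks of a geometric mean across genes, not of their Cts, and sets it beside mean expression. If relative quantities were meant, the rule on the Ct scale is the arithmetic mean and nothing is wrong. The Protocol also says that data are normalised on the PCR instrument, and what its software computes is not stated. This stands in part. The SAP can be read that way, although it starts from raw CT values and subtracts. The Protocol cannot easily be, because it names Ct. An analyst who codes the Protocol literally gets the wrong normaliser.

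The second reply is size, and it stands. A reader might infer that normalisation fails and that deltaCT simply tracks RNA yield. The calculations do not support that: about 96% to 99.7% of a common shift still cancels for the ordinary assumed Cts, and about 91% in the widest case. The larger figures need reference genes many cycles apart or very low Cts.

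The third reply is that no route to bias is documented, and this also stands. A reader might infer that the primary comparisons are biased. That needs yield to differ systematically by time or arm, and the documents report no yields. Allocation is randomised, and collection time and stabiliser volume are the same for all infants. The Protocol also drops samples in which any reference gene fails to amplify, which removes some of the lowest inputs.

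**Conclusion.** The Protocol's rule is wrong as written for a log scale, and the SAP does not say that anything else was done. The consequence is inexact cancellation and unequal gene weights, not a failure of normalisation. For a 3-cycle difference in yield, the error in deltaCT is hundredths to about a tenth of a cycle for ordinary spreads (0.5% to 7% in fold terms), and about 0.22 in the widest assumed set.

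These sizes rest on assumed reference Cts, equal two-fold amplification efficiency and a shift common to all genes. A biased time or treatment effect also requires yield to vary systematically by time or arm. The documents do not establish that, and they do not settle whether the literal rule was run. This is a minor point, worth correcting because the correction is nearly free.

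**What to change.** In the Protocol (Initial Gene Expression Analyses) and the SAP (Primary Outcome: Gene Expression), define the normaliser as the arithmetic mean of the reference-gene Ct values in each sample, equivalently the geometric mean of 2^-Ct. State which calculation was actually run.

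If it was the arithmetic mean, the wording change is enough. If it was the literal geometric mean of Ct, recompute deltaCT from the recorded Cts, rerun the primary ANOVA and report whether any conclusion changes. With the arithmetic mean the drift is exactly zero for any common shift.

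The cost is a sentence in each document and, if needed, one changed line of code and a rerun. No new assays are needed, provided that the individual reference Cts were kept, which the documents do not state.
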